5.4.3. Management of Dose-Limiting Toxicities or Other Urgent Situations

In all cases, investigators may employ any measures or concomitant medications, after discussion with the sponsor (whenever possible), necessary to optimally treat the subject.

5.4.4. Follow-Up of Dose-Limiting Toxicities

Any DLT should be followed until it resolves to baseline or appears to have stabilized for a minimum of 4 weeks (ie, 28 days). During follow-up, subjects should be seen as often as medically indicated to assure safety.

5.4.5. Procedures for Cohort Review and Dose Escalation

Telephone conferences will be scheduled by the sponsor with study investigators in order to review cohort-specific data and overall safety data, agree on dose escalation, adjudicate individual high-grade AEs as potentially dose-limiting, and guide other major study decisions.

5.4.6. Criteria and Procedures for Dose Interruptions and Adjustments of Study Drug

Treatment with study drug may be delayed to allow for resolution of toxicity. Subjects may resume treatment if no medical condition or other circumstance exists that, in the opinion of the investigator, would make the subject unsuitable for further participation in the study. For toxicities that occur outside of the 28-day DLT period, the treating investigator should contact the medical monitor to discuss the case of any subject whose treatment has been delayed for more than 4 weeks (28 days) before restarting treatment with study drug.

Instructions for dose modifications and interruptions are outlined in [Table 4](#). Individual decisions regarding dose interruptions and reductions should be made using appropriate clinical judgment in consultation with the medical monitor, taking into account relatedness of the AE to the study drug and the subject's underlying condition. Adverse events that have a clear alternative explanation, or transient (≤ 72 hours) abnormal laboratory values without associated clinically significant signs or symptoms, may be exempt from dose-reduction rules. Dose interruptions are permitted in the case of medical/surgical events or logistical reasons not related to study therapy (eg, elective surgery, unrelated medical events, subject vacation, holidays). Subjects should be placed back on study therapy within 4 weeks (28 days) of the scheduled interruption, unless otherwise discussed with the sponsor. The reason for interruption should be documented in the subject's study record.

Table 4: Rules for Interruption and Restarting of Study Drug

CTCAE Grade or Severity	Timing for Restarting Treatment	Dose Level for Restarting Treatment	Treatment Discontinuation ^a
1-2 (mild-moderate)	Continue treatment at the discretion of the investigator.	N/A	N/A
3 (severe)	Toxicity resolves to Grade 0-1.	Reduce by 1 dose level. ^b	Toxicity does not resolve within 4 weeks (28 days) of last dose, except by approval of the medical monitor. OR Second occurrence of previously resolved Grade 3 AE.
4 (life-threatening)	Permanently discontinue.	N/A	Permanently discontinue.

^a Permanently discontinue for any severe or Grade 3 AE that recurs or any life-threatening event.

^b No more than 2 dose reductions of study drug are permitted, or 1 dose reduction of study drug if the starting dose is 7 mg (see [Table 2](#)). Subject should be permanently discontinued from study drug if they have AEs requiring more than 2 dose reductions of study drug.

5.4.7. Definition, Procedures, and Supportive Care Guidelines for Immune-Related Adverse Events

INCAGN01949 is an immune modulator, and although no toxicities were identified in preclinical models, it is possible that irAEs (both nonserious and serious) similar to those described with approved immunotherapies may occur. Adverse events of a potential immunologic etiology or irAEs may be defined as an AE consistent with an immune phenomenon associated with drug exposure *after all other etiologies have been eliminated* (see [Section 8.8](#)). Immune-related AEs may be expected based on the nature of INCAGN01949, its mechanism of action, and reported experience with other immunotherapies. Special attention should be paid to AEs that may be suggestive of potential irAEs. An irAE can occur shortly after the first dose or several months after the last dose of treatment. Suspected irAEs should be discussed with the medical monitor when possible.

Subjects should receive appropriate supportive care measures as deemed necessary by the treating investigator. Suggested supportive care measures for the management of drug-related AEs with potential immunologic etiology are outlined in [Table 5](#). Detailed supportive care guidelines for specific irAEs can be found in [Appendix B](#). For each AE, attempts should be made to rule out other causes including, but not limited to, metastatic disease or bacterial or viral infection, which might require specific supportive care.

Table 5: Supportive Care Guidelines for Subjects Exhibiting Immune-Related Adverse Events

CTCAE Grade/Severity	Supportive Care ^a
Grade 1 (mild)	
 • Monitor symptoms and provide symptomatic treatment.
Grade 2 (moderate)	
 • Monitor symptoms and provide symptomatic treatment. • Consider consultation with specialists as necessary. • Consider systemic corticosteroids per institutional standard of care.
Grade 3-4 (severe–life-threatening)	
 • Monitor symptoms and provide symptomatic treatment. • Consider consultation with specialists as necessary. • Administer corticosteroids per institutional standard of care. • More potent immunosuppressive therapies should be considered for events not responding to systemic steroids after discussing with the medical monitor. • Study drug should be permanently discontinued for clinically significant or severe irAEs or for events where steroid course cannot be tapered below 7.5 mg/day prednisone or equivalent to manage symptoms.

^a Detailed supportive care guidelines for specific irAEs can be found in [Appendix B](#).

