5.4.9. Criteria for Permanent Discontinuation of Study Drug

The occurrence of unacceptable toxicity not caused by the underlying malignancy will be presumed to be related to study drug treatment and will require that the study drug be permanently discontinued. Unacceptable toxicity is defined as follows:

- Grade 4 or life-threatening AEs (see [Table 4](#) and [Table 6](#)).
- \geq Grade 2 ocular irAE.
- Occurrence of an AE that is related to treatment with the study drug that, in the judgment of the investigator or the sponsor's medical monitor, compromises the subject's ability to continue study-specific procedures or is considered to not be in the subject's best interest.
- An AE requiring more than 2 dose reductions of study drug, or more than 1 dose reduction if the starting dose is 7 mg (see [Table 2](#)).
- Persistent AE requiring a delay of therapy for more than 4 weeks (28 days), unless a greater delay has been approved by the sponsor.

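### For a first Grade 3 immune-related event that resolves, Protocol Table 4 allows restart one dose level lower while Table 5 says to stop permanently, and no text says which governs

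*Protocol*

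**What the plan says.** **Table 4 (Protocol 5.4.6)** sets interruption and restart rules by CTCAE grade and makes no exception for irAEs. In the Grade 3 row, labelled severe, the condition for restarting is "Toxicity resolves to Grade 0-1" and the dose instruction is "Reduce by 1 dose level". Discontinuation applies if the event has not resolved within 28 days of the last dose, unless the medical monitor approves otherwise, or if it occurs a second time. Footnote a reads: "Permanently discontinue for any severe or Grade 3 AE that recurs or any life-threatening event".

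**Table 5 (Protocol 5.4.7)** is specific to irAEs. Its Grade 3-4 row, headed severe to life-threatening, states: "Study drug should be permanently discontinued for clinically significant or severe irAEs". The same bullet adds events whose steroid course cannot be tapered below 7.5 mg/day of prednisone or equivalent.

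**Section 5.4.9** lists the toxicities that require permanent discontinuation. Grade 4 events and ocular irAEs of Grade 2 or higher are named; Grade 3 irAEs are not. Section 5.5.1 makes withdrawal from study drug mandatory for unacceptable toxicity and refers to Section 5.4 as a whole, which contains both tables.

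**Appendix B**, under Grade 3 or 4 endocrinopathies, allows hypothyroidism to be managed with hormone replacement and no interruption of treatment.

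**SAP Section 8.2.5** tabulates subjects with dose reductions, interruptions and permanent discontinuations due to treatment-emergent adverse events.

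**The concern.** Section 5.4.7 treats irAEs as an expected class of toxicity for this drug, so the case is foreseeable. An investigator whose patient has recovered from a first Grade 3 irAE finds a restart rule in one table and a permanent stop in the next.

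Three things depend on which is followed:

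- **Patient safety.** One patient is re-exposed and another with the same event is not, for no reason stated in the plan.
- **Reporting.** The same event enters the dose-reduction table at one site and the discontinuation table at another. The comparison across doses and tumor cohorts then partly reflects which page the site used.
- **Dose escalation.** Whether the patient receives the second planned dose in the first 28 days can affect DLT status under Table 3.

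**Working it through.** The plan gives no figure to reproduce here, so the check is to set the passages side by side.

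| Event | Table 4 | Table 5 | Section 5.4.9 | Agree? |
|---|---|---|---|---|
| First Grade 3 irAE, resolved to Grade 0-1 within 28 days of last dose | Restart one level lower | Stop permanently if clinically significant or severe | Not listed by grade | No |
| Grade 3 irAE that recurs | Stop | Stop | Not listed by grade | Tables agree |
| Grade 3 irAE unresolved at 28 days, no monitor approval | Stop | Stop | Stop if therapy is delayed beyond 28 days without sponsor approval | Yes |
| Grade 4 irAE | Stop | Stop | Stop | Yes |
| Grade 3 or 4 hypothyroidism judged an irAE | Grade 3: hold, then restart; Grade 4: stop | Stop | Grade 4: stop | No; Appendix B adds no interruption |

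**Can a definition remove the first-row conflict?** Only if severe meant something other than Grade 3. Table 4 labels Grade 3 severe, the Table 5 row header does the same, and the grading scale in Section 8.1.2 describes Grade 3 as severe. On the protocol's own terms a Grade 3 irAE is a severe irAE.

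**Is there a precedence rule?** None appears in Sections 5.4.6, 5.4.7, 5.4.9, 5.5.1 or Appendix B. The Grade 4 item in 5.4.9 refers to Tables 4 and 6, not Table 5.

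**Does it reach the DLT count?** Under 14-day cycles the planned doses in Days 1 to 28 fall on Day 1 and Day 15, so two are planned. Suppose a Grade 3 irAE begins before Day 15 and improves to Grade 1 in under 5 days.

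1. Under the immune-related row of Table 3 it is not a DLT.
2. Following Table 4, the Day 15 dose may be given one level lower, after discussion with the medical monitor as Section 4.1.1.1 asks. Two of 2 doses are given.
3. Following Table 5, drug is stopped. One of 2 doses is given, and the general row of Table 3 counts planned doses missed because of toxicity as a DLT, whatever the grade.

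One such change matters under the 3 + 3 rule. In the first three subjects, 0/3 escalates and 1/3 expands the cohort. In an expanded cohort, 1/6 = 16.7% allows escalation and 2/6 = 33.3% reaches the one-third limit.

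This route is conditional. The nonhematologic row of Table 3 may already make the Grade 3 event a DLT, in which case the choice of table changes nothing. An event starting after the Day 15 dose is also unaffected, because both planned doses have been given.

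**The case against.** **Table 5 is advisory.** It is introduced with "Suggested supportive care measures for the management of drug-related AEs with potential immunologic etiology are outlined in" Table 5, and its verb is should. Table 4 is the titled rule for interruption and restarting, and Section 5.4.6 adds: "Individual decisions regarding dose interruptions and reductions should be made using appropriate clinical judgment in consultation with the medical monitor". Suspected irAEs are also to be discussed with the monitor when possible. This softens the conflict and makes opposite handling less likely. It does not say which table governs.

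**Table 5 may mean only a subset of Grade 3 irAEs.** The steroid-taper clause would add little if every Grade 3 irAE were already stopped, and Appendix B's hypothyroidism text points the same way. This is a fair reading, but the row header equates Grade 3 with severe and no subset is defined.

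**Section 5.4.9 has a judgment clause.** A related event can be stopped if it compromises study procedures or the subject's best interest. That permits stopping in individual cases; it does not settle the general rule.

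**The ocular criterion.** A reader might infer a second contradiction, because Table 4's Grade 1-2 row says "Continue treatment at the discretion of the investigator" while Section 5.4.9 names, at that grade or higher, a "Grade 2 ocular irAE" as a reason to stop. The documents do not support calling this unresolved. Sections 5.4.9 and 5.5.1 make the stop mandatory by name, Table 3 makes the same event a DLT, and a general discretion to continue is limited by a specific mandatory stop. What remains is a missing cross-reference in Table 4.

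**Conclusion.** The inconsistency is real and narrow. It applies to a first Grade 3 irAE that resolves to Grade 0-1 within 28 days of the last dose, with Appendix B adding a third instruction for hypothyroidism. It rests on reading severe as Grade 3, as both tables do, and on the absence of any precedence statement. The effect on DLT status is possible but not established.

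Three stronger conclusions should not be drawn.

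- **That every Grade 3 irAE is affected.** Recurrent events, and those unresolved at 28 days without medical monitor approval, stop under both tables.
- **That the effect can be sized at roughly 6 to 33 percentage points.** Those figures are 1/17 = 5.9% and 1/3 = 33.3%, which describe any single event in cohorts of 17 and 3. They contain no irAE rate, and the documents give none.
- **That stopped subjects no longer contribute scans or adverse events.** Sections 6.4.2 and 7.7.1.1.3 continue imaging after discontinuation for reasons other than progression. Section 6.4.1 continues adverse event reporting for at least 60 days after the last dose, although Section 8.1.2 ends monitoring for new events when a new anticancer therapy starts. What is lost is later on-treatment observation.

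The sponsor should correct this because conflicting instructions on stopping drug concern patient safety and the correction is cheap. It does not invalidate any planned analysis.

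**What to change.** Reconcile Tables 4 and 5, Section 5.4.9 and Appendix B so that they give one instruction for Grade 3 irAEs, including how hypothyroidism is handled, and state which passage prevails when an event falls under more than one. Which instruction is right is for the sponsor's clinical team; this review takes no position. When the text is settled, check its consequence for the missed-dose row of Table 3.

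As a secondary edit, add a cross-reference in Table 4's Grade 1-2 row to the ocular irAE criterion in Section 5.4.9.

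The cost is clarifying wording in a protocol amendment. No sample size, analysis method or SAP table needs to change.

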5.4.8. Management of Infusion Reactions

[Table 6](#) shows treatment guidelines for subjects who experience an infusion reaction associated with study drug administrative procedures. Signs and symptoms usually develop during or shortly after drug infusion and generally resolve completely within 24 hours of completion of infusion.

Table 6: INCAGN01949 Infusion Reaction Treatment Guidelines

CTCAE Grade	Treatment	Premedication at Subsequent Dose Administration

Grade 1: Mild reaction; infusion interruption not indicated; intervention not indicated.
	
Increase monitoring of vital signs as medically indicated until the subject is deemed medically stable in the opinion of the investigator.
	
None.

Grade 2: Requires infusion interruption but responds promptly to symptomatic treatment (eg, antihistamines, NSAIDs, narcotics, IV fluids); prophylactic medications indicated for ≤ 24 hours.
	
Stop infusion and monitor symptoms. Additional appropriate medical therapy may include but is not limited to the following:
 
 • IV fluids • Antihistamines • NSAIDs • Acetaminophen • Narcotics 
Increase monitoring of vital signs as medically indicated until the subject is deemed medically stable in the opinion of the investigator.
 
If symptoms resolve within 1 hour of stopping drug infusion, the infusion may be restarted at 50% of the original infusion rate. Otherwise, dose administration will be interrupted until symptoms resolve, and the subject should be premedicated for the next scheduled dose.
 
Subjects who develop Grade 2 toxicity despite adequate premedication should be permanently discontinued from further study drug administration.
	
Subject may be premedicated 1.5 h (± 30 min) before infusion with the following:
 
 • Diphenhydramine 50 mg orally (or equivalent dose of antihistamine). • Acetaminophen 500-1000 mg orally (or equivalent dose of antipyretic).

Grade 3: Prolonged (ie, not rapidly responsive to symptomatic medication and/or brief interruption of infusion); recurrence of symptoms following initial improvement; hospitalization indicated for other clinical sequelae (eg, renal impairment, pulmonary infiltrates).
	
Stop infusion. Additional appropriate medical therapy may include but not be limited to the following:
 
 • IV fluids • Antihistamines • NSAIDs • Acetaminophen • Narcotics • Oxygen • Pressors 	
No subsequent dose.

Grade 4: Life-threatening; pressor or ventilatory support indicated.
	
 • Corticosteroids • Epinephrine 
Increase monitoring of vital signs as medically indicated until the subject is deemed medically stable in the opinion of the investigator.
 
Hospitalization may be indicated.
 
Subject is permanently discontinued from further study drug administration.
	

NSAID = nonsteroidal anti-inflammatory drug.

Note: Appropriate resuscitation equipment should be available in the room and a physician readily available during study drug infusion.

5.4.9. Criteria for Permanent Discontinuation of Study Drug

The occurrence of unacceptable toxicity not caused by the underlying malignancy will be presumed to be related to study drug treatment and will require that the study drug be permanently discontinued. Unacceptable toxicity is defined as follows:

- Grade 4 or life-threatening AEs (see [Table 4](#) and [Table 6](#)).
- \geq Grade 2 ocular irAE.
- Occurrence of an AE that is related to treatment with the study drug that, in the judgment of the investigator or the sponsor's medical monitor, compromises the subject's ability to continue study-specific procedures or is considered to not be in the subject's best interest.
- An AE requiring more than 2 dose reductions of study drug, or more than 1 dose reduction if the starting dose is 7 mg (see [Table 2](#)).
- Persistent AE requiring a delay of therapy for more than 4 weeks (28 days), unless a greater delay has been approved by the sponsor.

5.4.10. Treatment After Initial Evidence of Radiologic Disease Progression

Immunotherapeutic agents may produce antitumor effects by potentiating endogenous cancer-specific immune responses. The response patterns seen with such an approach may extend beyond the typical time course of responses seen with cytotoxic agents and may manifest as a clinical response after an initial increase in tumor burden or even the appearance of new lesions.

If radiologic imaging shows disease progression, then subjects have the option to continue treatment while awaiting radiographic confirmation of progression as outlined in [Section 7.7.1](#).

5.5. Withdrawal of Subjects From Study Treatment

5.5.1. Withdrawal Criteria

A subject may choose to withdraw from the study at any time or be withdrawn by the investigator or sponsor, if the subject is noncompliant with the study requirements. Subjects may also be withdrawn at the discretion of the FDA or health authorities. If a subject is withdrawn, then every reasonable effort should be made to determine the reason for withdrawal, and this information should be recorded in the electronic case report form (eCRF).

Subjects **must** be withdrawn from **study drug** for the following reasons:

- The subject becomes pregnant.
- Consent is withdrawn. Subjects may choose to withdraw from the study at any time without penalty of jeopardizing their health care or loss of benefits to which the subject is otherwise entitled.
- Further participation would be injurious to the subject's health or well-being, in the investigator's medical judgment.
- The subject is lost to follow-up.

- Unacceptable toxicity (see [Section 5.4](#)). Subjects with unacceptable toxicities must be withdrawn from study drug but will continue to be followed during the safety follow-up visits as specified in [Section 6.4](#).
- The study is terminated by the sponsor.
- The study is terminated by the local health authority, IRB, or IEC.

A subject **may** be discontinued from study treatment as follows:

- Confirmed radiographic progression of disease per mRECIST v1.1. See [Section 7.7.1](#).

Note: For unconfirmed progression, see [Section 7.7.1](#).

Note: A subject may be granted an exception to continue on treatment with confirmed radiographic progression if clinically stable or clinically improved. See [Section 7.7.1](#).

- If, during the course of the study, a subject is found not to have met eligibility criteria (see [Section 3](#)), then the medical monitor, in collaboration with the investigator, will determine whether the subject should be withdrawn from the study.
- If a subject is noncompliant with study procedures or study drug administration in the investigator's opinion, then the sponsor should be consulted for instruction on handling the subject.

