If repeat imaging shows < 20% tumor burden compared with nadir, stable or improved previous new lesion (if identified as cause for initial disease progression), and stable/improved nontarget disease (if identified as cause for initial disease progression), then treatment may be continued or resumed. If repeat imaging confirms disease progression due to any of the scenarios listed below, then subjects will be discontinued from study therapy. However, if a subject has confirmed radiographic progression (ie, 2 scans at least 4 weeks but no later than 6 weeks apart demonstrating progression) per mRECIST, but the subject is achieving a clinically meaningful benefit, then an exception to continue treatment may be considered after consultation with the medical monitor. Clinically stable subjects at the confirmatory scan should also have no further increase in the target lesions, no unequivocal increase in nontarget lesions, and no additional new lesions develop (nonworsening disease progression) to continue study treatment (see [Section 7.7.1](#)).

In determining whether or not the tumor burden has increased or decreased, site study teams should consider all target lesions as well as nontarget lesions (refer to RECIST v1.1 guidelines).

Scenarios where disease progression is confirmed at repeat imaging include the following:

- Tumor burden remains $\geq 20\%$ and at least 5 mm absolute increase compared with nadir.
- Nontarget disease resulting in initial disease progression is worse (qualitative).
- New lesion resulting in initial disease progression is worse (qualitative).
- Additional new lesion(s) are found since last evaluation.

When feasible, subjects should not be discontinued until progression is confirmed. This allowance to continue treatment despite initial radiologic progression takes into account the observation that some subjects can have a transient tumor flare in the first few months after the

start of immunotherapy, but with subsequent disease response. Subjects who are deemed clinically unstable are not required to have repeat imaging for confirmation of disease progression.

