7.7. Efficacy Assessments

7.7.1. Modified RECIST v1.1 Assessment of Disease

Modified RECIST will be applied by the site as the primary measure for assessment of tumor response and as a basis for Protocol guidelines related to disease status (eg, discontinuation of study therapy). Unique tumor responses have been noted with immunotherapy treatment (Chiou and Burotto 2015); therefore, RECIST v1.1 has been adapted for use in this study and referred to as mRECIST (see Section 1.3.3.1).

If radiologic imaging shows progressive disease, then tumor assessment should be repeated at a minimum of 4 weeks, but no later than 6 weeks later to confirm progression, with the option of continuing treatment while awaiting radiologic confirmation of progression. Table 12 provides instructions on how to proceed with treatment based on the subject's clinical status once the initial scan showing radiologic evidence of progression is observed.

Subjects may receive treatment while waiting for confirmation of progression if they are clinically stable as defined by the following criteria:

- Absence of clinically significant signs and symptoms (including worsening of laboratory values) indicating disease progression.
- No decline in ECOG performance status.
- Absence of rapid progression of disease.
- Absence of progressive tumor at critical anatomical sites (eg, cord compression) requiring urgent alternative medical intervention.

Table 12: Imaging and Treatment After First Radiologic Evidence of Progressive Disease

	Clinically Stable		Clinically Unstable	
	Tumor Imaging	Treatment	Tumor Imaging	Treatment
First radiologic evidence of progression	Repeat imaging 4-6 weeks to confirm progression	May continue study treatment at the investigator's discretion while awaiting confirmatory tumor imaging	Repeat tumor imaging 4-6 weeks to confirm progression per physician discretion only	Discontinue treatment
Repeat scan confirms progression	No additional tumor imaging required	Discontinue treatment	No additional tumor imaging required	N/A
Repeat scan shows SD, PR, or CR	Continue regularly scheduled tumor imaging assessments	Continue study treatment at the investigator's discretion	Continue regularly scheduled tumor imaging assessments	May restart study treatment if condition has improved and/or clinically stable per investigator's discretion

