As noted above, if disease progression is observed, then the study site may elect to continue treatment; repeat imaging at a minimum of 4 weeks, but no later than 6 weeks later; and assess tumor response or confirmed progression per mRECIST.

In determining whether or not the tumor burden has increased or decreased, study site investigators should consider all target lesions as well as nontarget lesions. Subjects that are deemed clinically unstable are not required to have repeat tumor imaging for confirmation. If radiologic progression is confirmed by subsequent scan, then the subject should be discontinued from study treatment. If radiologic progression is not confirmed, then the subject should resume or continue study treatment and have the next tumor imaging according to the Protocol schedule (see Table 7). If progression is not confirmed and the subject continues on treatment, then the next scan that documents disease progression (and is confirmed by a second scan at least 4 weeks but no later than 6 weeks later) will be considered the date of disease progression.

If a subject has confirmed radiographic progression (ie, 2 scans at least 4 weeks, but no later than 6 weeks apart demonstrating progression) per mRECIST, but the subject is achieving a clinically meaningful benefit, an exception to continue treatment may be considered after consultation with the medical monitor. Clinically stable subjects at the confirmatory scan should also have no further increase in the target lesions, no unequivocal increase in nontarget lesions, and no additional new lesions develop (nonworsening disease progression) to continue study treatment.

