7.7.1.1.2. Tumor Imaging During the Study

The first imaging assessment should be performed 8 weeks after the first dose of study drug, every 8 weeks (56 days \pm 7 days) for 12 months, and then every 12 weeks (84 days \pm 7 days) thereafter until disease progression is determined. Imaging assessments may be performed more frequently if clinically indicated. **Imaging should not be adjusted for delays in cycle starts.**

Per mRECIST v1.1, response should be confirmed by a repeat radiographic assessment not less than 4 weeks from the date that the response was first documented. The scan for confirmation of response may be performed at the earliest of 4 weeks after the first indication of response or at the next scheduled scan, whichever is clinically indicated.

Imaging should continue to be performed until documented disease progression, the start of new anticancer treatment, withdrawal of consent, death, or the end of the study, whichever occurs first. Disease progression should be confirmed at least 4 weeks, but no later than 6 weeks after the first scan indicating progression in clinically stable subjects. Subjects who have unconfirmed disease progression may continue on treatment until progression is confirmed, provided that they have met the conditions detailed in [Section 7.7.1](#). A central imaging vendor will not be used in this study.

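### Section 5.5.1 makes stopping at confirmed progression optional and states a looser exception test than Sections 1.3.3.1.1 and 7.7.1

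*Protocol*

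**What the plan says.** Section 5.5.1 of the protocol has two lists. One gives the reasons for which a subject *must* be withdrawn from study drug; the other gives those for which a subject *may* be discontinued. Confirmed radiographic progression per mRECIST v1.1 is in the second list only. A Note under it reads: "A subject may be granted an exception to continue on treatment with confirmed radiographic progression if clinically stable or clinically improved". The progression item and both of its Notes refer the reader to Section 7.7.1.

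Elsewhere the protocol treats stopping as the rule:

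- Section 1.3.3.1.1: "If repeat imaging confirms disease progression due to any of the scenarios listed below, then subjects will be discontinued from study therapy".
- Section 7.7.1: "If radiologic progression is confirmed by subsequent scan, then the subject should be discontinued from study treatment".
- Table 12, row for a repeat scan that confirms progression, clinically stable column: "Discontinue treatment".

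Sections 1.3.3.1.1 and 7.7.1 then describe a narrow way to continue. Where the subject has a clinically meaningful benefit, "an exception to continue treatment may be considered after consultation with the medical monitor". A radiographic condition follows: "Clinically stable subjects at the confirmatory scan should also have no further increase in the target lesions", together with no unequivocal growth of nontarget lesions and no further new lesions.

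**The concern.** The same event carries a different default action and a different exception test depending on which section a site opens. A site that works from the withdrawal list in 5.5.1 could take clinical stability as enough to keep a subject on drug. A site that works from 7.7.1 would also need benefit, consultation and a scan that is no worse.

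The subjects concerned have had progression documented on two scans and are receiving an experimental antibody. Section 5.6.3 bars other anticancer medication during treatment. Inclusion criterion 4 admits subjects who refused standard treatment, so some may have other options. The rule for when they come off drug should read the same everywhere.

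**Working it through.** The documents give no figure on this point and no arithmetic applies. The check sets the sections side by side.

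**Step 1. Which section a site is sent to.** Sections 4.4 and 5.2.1 let a subject stay on drug while benefiting and until a withdrawal condition is met. Both point to Section 5.5 for those conditions. Neither points to 7.7.1 or 1.3.3.1.1.

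**Step 2. Default action and conditions for an exception.**

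| Place | Default at confirmed progression | Meaningful benefit required | Medical monitor consulted | Nonworsening lesions (if clinically stable) |
|---|---|---|---|---|
| 1.3.3.1.1 | Stop (*will*) | Yes | Yes | Yes |
| 7.7.1 text | Stop (*should*) | Yes | Yes | Yes |
| Table 12 | Stop | No exception shown | – | – |
| 5.5.1 | Optional (*may*) | Not named | Not named | Not named |

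Three places make stopping the default and one makes it optional. The 5.5.1 Note requires only that the subject be clinically stable or improved.

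**Step 3. Whether the two tests can give different answers.** Section 1.3.3.1.1 lists the findings that confirm progression; one is an additional new lesion since the last evaluation. Section 7.7.1 describes clinical stability as no significant signs or symptoms of progression, no ECOG decline, no rapid progression, and no progressive tumor at a critical site. Assume the 5.5.1 Note uses the term in that sense, since it gives no other. A subject with a slow, symptom-free additional new lesion at a noncritical site is then clinically stable:

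- Under the 5.5.1 Note, an exception may be granted.
- Under 7.7.1, the condition on additional new lesions is not met, so the subject should stop.

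The tests differ for a subject the protocol itself anticipates.

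**Step 4. Endpoints.** SAP Sections 7.4.4.2 and 7.4.8.2 close mRECIST duration of response and PFS at the first confirmed PD. The footnotes to shell Tables 2.2.1 and 2.2.2 close mRECIST best response at the same point. Treatment after confirmed progression moves none of these.

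**Step 5. Imaging for a subject kept on drug.** Section 7.7.1.1.2 ends the scan schedule with "thereafter until disease progression is determined" and says again: "Imaging should continue to be performed until documented disease progression". The synopsis also stops at progression. Table 7 footnote j gives the interval and no end point. Table 12 requires no further imaging, but in a row that assumes drug is stopped. No passage states a schedule for a subject who continues under the exception.

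**The case against.** The best defense is that 5.5.1 is only a pointer. It refers to 7.7.1 three times in three lines. Calling continuation an exception that is granted implies that stopping is the norm and that someone approves the departure, and 7.7.1 brings in the medical monitor. The *may* list collects case-by-case decisions, and its other two items also go to the medical monitor or sponsor. Section 7.7.1 itself says *should*, not *must*.

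Other controls also remain. Sections 4.4 and 5.2.1 let any subject continue only while deriving benefit, withdrawal is mandatory if participation would be injurious, and each cycle includes examination, ECOG status, laboratory tests and AE review.

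Much of this stands. The cross-references soften the inconsistency, and the benefit condition in 4.4 and 5.2.1 covers part of what the Note leaves out. What remains is that the Note states its own condition before it refers onward, and that this condition omits the consultation and the lesion criteria. A reader sent from 4.4 or 5.2.1 to Section 5.5 meets a permissive list first.

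A reader might go further and infer that the protocol contradicts itself on whether such subjects must be scanned, setting Table 7 footnote j against 7.7.1.1.2. The text does not support that. Every passage that gives an end point for on-treatment imaging puts it at progression. Footnote j is silent on the end point, and Section 6 sends the reader to Section 7 for instructions on each assessment. This is a gap, not a conflict, so a count of scans in dispute would have nothing to rest on. Section 7.7.1.1.2 also allows more frequent imaging when clinically indicated, so scans are not barred.

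**Conclusion.** The inconsistency in the stopping rule is real and should be corrected. Section 5.5.1 makes discontinuation optional where three other places make it the default, and its exception test omits meaningful benefit, consultation and the lesion conditions. The two tests give opposite answers for a clinically stable subject with an additional new lesion, reading clinical stability as 7.7.1 defines it.

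The size is qualitative. The documents do not say how many subjects would be granted the exception, and the controls already in place limit the harm. The effect is on subject protection and on consistency between sites. A reader might infer bias in efficacy results; the SAP does not support that, because mRECIST PFS, duration of response and best response all close at first confirmed PD.

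Separately, and only as a clarification, no imaging schedule is stated for subjects kept on drug under the exception.

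**What to change.** 1. In Section 5.5.1, move the item to the list of mandatory withdrawals from study drug, worded: *Confirmed radiographic progression per mRECIST v1.1, unless the exception in Section 7.7.1 is granted.* Keep the Note on unconfirmed progression with it. Delete the Note that states a separate test.
2. In Table 12, row for a repeat scan that confirms progression, clinically stable column, add a footnote pointing to the Section 7.7.1 exception.
3. Optionally, state what imaging applies while a subject continues under the exception. The sponsor may continue the scheduled scans or leave imaging to clinical indication; either is reasonable. Continuing them adds procedures for those subjects without changing any mRECIST endpoint.

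Items 1 and 2 cost amendment text only. They add no new stopping rule, keep treatment beyond progression available, and leave the decision with the investigator and medical monitor under 7.7.1. The verbs would still differ (*must* in 5.5.1, *will* in 1.3.3.1.1, *should* in 7.7.1). All three would then lead to the same action with the same exception, and the sponsor could align them in the same amendment.
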